4. SAMPLE SIZE

An arbitrary cohort of 200 children has been chosen. A cohort of 100-exposed and 100-not exposed patients is anticipated to allow to demonstrate the interest of using Healsea® Children in the allergic paediatric population.

Indeed, 100 patients by arms are enough to detect a Cohen's effect size of 0.4 with a power of 80% and a type I error of 5%. Cohen's effect size is defined as the standardized difference between AUC in groups. Following Cohen's methodology, 0.4 is an intermediate size between a small effect (0.2) and a medium effect (0.5) and is coherent with the expected result.

5. DEFINITION OF THE ANALYSIS SETS

Screened subjects: all subjects who signed an informed consent.

Included subjects: all screened subjects who participated in the study.

Full Analysis Set (FAS): all included subjects who used the investigational medical device at least once.

Per-Protocol (PP) Set: Efficacy population based on the FAS without patients with major protocol deviations.

Safety and Efficacy analyses will be performed on the FAS.

The analyses of the primary and one secondary (modelling of AUC on total WURSS by multivariate ANCOVA) efficacy criteria will also be performed on the PP Set.

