8.2 Investigational device and comparator

The investigational device which is Healsea® Children. This is a CE marked Medical Device. Patients/parents will be allowed to use or not the investigational nasal spray. If they choose nasal symptoms to be treated with Healsea® Children, they will start the nasal spray treatment following

Page **31** of **61** Version: 2.0; 08 Sep 2021

their inclusion visit (Visit 1). Healsea® Children will be used on the top of conventional therapies for common cold and administered with the help of an adult, spraying one puff (1-2 sec) twice a day in each nostril for 10 days.

No comparator is used in this study. Patient/parents who prefer not to use Healsea® Children will use conventional therapies for common cold only. **However, use of nasal irrigation will not be authorized for these patients.**

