9.2 Study population

The study population consists in all the patients included and who do not meet a "major deviation to protocol" as defined in section 12.

The safety population consists in all the patients included in this study.

Version: **2.0**; **08 Sep 2021** Page **38** of **61**

The analysis of primary and secondary endpoints will be performed on study population, safety endpoint will be performed on safety population.

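### The SAP's Full Analysis Set requires use of the device, so as written it excludes the conventional-therapy group from every efficacy and safety analysis

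*SAP*

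**What the plan says.** SAP section 5 sets up a chain of populations.

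- Included subjects carry no exposure condition: "Included subjects: all screened subjects who participated in the study".
- The next step adds one: "Full Analysis Set (FAS): all included subjects who used the investigational medical device at least once".
- The Per-Protocol Set inherits it: "Per-Protocol (PP) Set: Efficacy population based on the FAS without patients with major protocol deviations".
- Both efficacy and safety then rest on that set: "Safety and Efficacy analyses will be performed on the FAS".

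Protocol 8.2 describes the comparison group: "Patient/parents who prefer not to use Healsea® Children will use conventional therapies for common cold only". The sample-size section of the SAP plans the two groups by exposure: "A cohort of 100-exposed and 100-not exposed patients is anticipated".

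Protocol 9.2 defines its populations without reference to device use. Efficacy covers included patients who have no major deviation. For safety, "The safety population consists in all the patients included in this study". SAP section 12, which records changes from the protocol, covers only the definition of symptom duration.

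**The concern.** Not using the device is what defines the comparison group, and using it is what admits a child to the Full Analysis Set. The two conditions exclude each other, so the rule removes the control group from the analysis that is meant to compare it with Healsea. The Per-Protocol Set offers no fallback because it is a subset.

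The stakes are high because SAP 6.3.1 treats only the primary criterion as conclusive, and its primary population is the one that is wrongly specified. If the text is not corrected, whoever prepares the analysis has to decide what the rule should have been. This is an open-label study, and SAP section 12 already describes, in the past tense, how several patients answered their diaries. Some study data had therefore been seen when that text was written. Protocol 10.3 requires decisions on evaluability to be made and documented before database lock, so the replacement rule should be in writing by then.

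**Working it through.** **1. The plan's own figure.** Inputs from SAP sections 4 and 6.3.1: standardised difference d = 0.4, power 80%, two-sided alpha 0.05, equal groups.

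- Normal approximation: n per group = 2 × (1.960 + 0.842)² / 0.4² = 2 × 7.85 / 0.16 ≈ 98.1, rounded up to 99.
- Two-sample t-test: 99.08, rounded up to 100.
- Power at 100 per group: 80.7% (normal approximation) or 80.4% (t-test).

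The stated 100 per group reproduces and is not in dispute. It presupposes about 100 children in each group.

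**2. The set definitions applied to the planned cohort.**

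| Set | Healsea chosen | Conventional therapy chosen |
|---|---|---|
| Included (SAP 5) | 100 | 100 |
| Full Analysis Set as written | up to 100 | 0 |
| Per-Protocol Set (subset of the above) | up to 100 | 0 |

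The only literal exception is a child who chose conventional therapy and used the spray anyway. With a control count of 0, the standard error of the difference, SD × √(1/n₁ + 1/n₂), contains 1/0. The t-test, the Wilcoxon alternative and the treatment term in every model are then undefined.

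**3. Which analyses depend on the set.** The primary test (10.1) and the ANCOVA (10.2.1) use the Full Analysis Set and the Per-Protocol Set. The Cox models (10.2.2), the logistic and Poisson models (10.2.3 to 10.2.5), concomitant treatments (10.3), non-related adverse events (10.4) and safety (11) use the Full Analysis Set. Disposition, deviation and withdrawal outputs use screened or included subjects and are unaffected.

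**4. The SAP against itself.** Section 8 describes baseline data on the Full Analysis Set by treatment group. The mock disposition table has Full Analysis Set and Per-Protocol Set rows with a conventional-therapy column. One major deviation in section 7.2, nasal irrigation by a child who chose not to take Healsea, would have almost nobody to apply to in a set of device users.

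**5. The charitable reading.** Suppose the use condition binds only the Healsea group.

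- A child who chose Healsea and never sprayed is removed on a post-baseline event. No control child can be removed in this way.
- SAP section 9 computes compliance as uses × 100 / 20, so a never-user has 0 × 100 / 20 = 0%. Section 7.2 classes compliance outside 80% to 120% as minor, which does not exclude a child from the Per-Protocol Set. Section 5 nevertheless removes the same child from both sets.
- The documents give no share of never-users. Assume 0% to 10%. At 0% nothing changes. At 10% the comparison is 90 against 100. Then d / √(1/90 + 1/100) = 0.4 / 0.1453 = 2.753, and power = Φ(2.753 − 1.960) ≈ 79%, against about 81% at 100 per group.

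The loss of power is small. The issue on this reading is selection in one group only.

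**The case against.** The strongest reply is that nobody would apply the sentence literally. The mock tables carry control columns, baseline is described by group, the primary test compares the groups, compliance is qualified as applying to Healsea users, and populations are settled at the data review before lock. On this view the fault is a missing qualifier, and an impossible primary test is the least likely outcome. That is right about intent, and actual exclusion of the controls is unlikely. It does not supply a correct rule, however, because nothing elsewhere in the SAP redefines the set.

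Three narrower points also have force.

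- **Safety.** SAP 11.2 counts only events not judged unrelated to the device. Unexposed children would be expected to contribute few or none, so the safety loss is mainly denominators and study duration.
- **One-sided exclusion.** Under the charitable reading its size rests on an assumed share of never-users, no bias has been calculated, and the effect may be nil.
- **Protocol 9.2.** The protocol removes major deviators from its efficacy population and the SAP's Full Analysis Set does not. In that respect the SAP is the more inclusive document, and the deviation-free set survives as the Per-Protocol Set. The change still had to be recorded.

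**Conclusion.** The concern holds: the definition is wrong as written and must be corrected. Taken literally it gives up to 100 Healsea children against 0 controls, crossovers aside, in both the Full Analysis Set and the Per-Protocol Set, and the primary objective cannot be answered. Read charitably it removes never-users from one group only, which mixes an as-treated group with a group of all choosers. On an assumed share of 0% to 10%, that costs at most about two percentage points of power and adds a selection of unknown, probably modest, size. Either way the SAP departs from protocol 9.2 without saying so. The conclusion on the literal rule rests on the documents' definitions alone; only the charitable-reading figures depend on the assumed share.

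**What to change.** In SAP section 5:

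- Define the Full Analysis Set as all included subjects, grouped by the treatment choice recorded at Visit 1, whether or not the device was used. Protocol 9.1 already groups by chosen treatment.
- Define a separate safety set as all included subjects, in line with protocol 9.2.
- Derive the Per-Protocol Set from the corrected Full Analysis Set. It then matches the efficacy population of protocol 9.2.
- Keep the condition of at least one use only for the Healsea exposure and compliance table.

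In SAP section 12, state that the main efficacy set differs from protocol 9.2 because major deviators are retained, and that the protocol's population is reported as the Per-Protocol Set. Date the change and complete it before database lock.

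The cost is a few lines of wording. The choice at Visit 1 is already collected, and no further data or patients are needed. With 100 children per group in the corrected set, the planned power of about 80% applies as intended.

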6. STATISTICAL METHODS

6.1. Data processing

The analyses will be computed with SAS Version 9.4 TS Level 1M6 Copyright (c) 2016 by SAS Institute Inc., Cary, NC, USA.

6.2. Description

The number of available data and/or the number of missing data will be given and the following descriptive statistics will be provided:

- For quantitative parameters: mean, standard deviation, median, Q1, Q3, extreme values (min and max).

In this case, calculated statistics (mean, standard deviation, median, Q1, Q3) will generally be displayed with one more significant figure than the observed data, unless the described variable necessitates less precision.

- For qualitative parameters: number and percentage of each modality.

Usually, one decimal digit will be given. A second decimal digit could be provided to improve the display, if required.

6.3. Statistical/Analytical issues

6.3.1. Significance level

All statistical analyses will be performed at the 0.05 global significance level (type I error rate), using two-sided tests.

The statistical results are conclusive for the primary efficacy criterion.

All the other statistical results have to be considered within a descriptive perspective and not as inferential issues. No adjustment for Type I error is done. P-values of statistical tests will be provided for information only.

6.3.2. Interim analysis

No interim analysis will be performed.

6.3.3. Handling of dropouts and missing data

a) Repositioning of visits

Not applicable.

b) Partially filled scales and missing data (other than WURSS-K questionnaire and dates)

Concerning dates and WURSS-K questionnaire, see §6.4.

No imputation will be done. Missing data will not be estimated and will be treated as missing data for the statistical analysis.

c) Dropouts

Subjects from Full Analysis Set who prematurely discontinued the study will be included in the analysis.

Except for WURSS-K questionnaire and dates, no method will be applied to replace missing data.

6.4. General conventions and calculated variables**6.4.1. Subject reference start/end dates**

For each subject, the reference dates will be the following:

- The reference start date is the date of inclusion visit.
- The reference end date is the date when subject was determined to have ended the trial.

6.4.2. Computation of a duration

The formulae below will be generally used:

- Duration (in days) = Date#2 – Date#1 + 1 day

6.4.3. Missing dates of inclusion visit or end of study

Missing dates of inclusion visit and of end of study will be reviewed by the members of the Validation Committee and extrapolated using all information recorded.

6.4.4. Missing start/end dates of adverse events / incidents / expected side effects

In the following paragraphs, adverse events, incidents and expected side effects will be referred to as “adverse events” for ease of reading.

a) Start date

Completely missing date: it will be estimated by the reference start date.

If the day and the month are missing:

- If the year = year of reference start date, it will be estimated by the reference start date
- If the year < year of reference start date, it will be estimated by the 31st December
- If the year > year of reference start date, it will be estimated by the 1st January

If only the day is missing:

- If the month/year = month/year of reference start date, it will be estimated by the date of reference start date
- If the month/year < month/year of reference start date, it will be estimated by the last day of the month
- If the month/year > month/year of reference start date, it will be estimated by the first day of the month

If after imputation, the estimated start date is after the end date of the adverse event, it will be replaced by the end date of the adverse event.

b) End date

Note: the following rules concern events that are not “ongoing” at the end of the study.

Completely missing date: it will be estimated by the reference end date

If the day and the month are missing:

- If the year = year of reference end date, it will be estimated by the reference end date
- If the year < year of reference end date, it will be estimated by the 31st December
- If the year > year of reference end date, it will be estimated by the 1st January

If only the day is missing:

- If the month/year = month/year of reference end date, it will be estimated by the reference end date
- If the month/year < month/year of reference end date, it will be estimated by the last day of the month
- If the month/year > month/year of reference end date, it will be estimated by the first day of the month

If after imputation, the estimated end date is before the start date of the adverse event, it will be replaced by the start date of the adverse event.

6.4.5. Missing start/end dates of concomitant medications

Same rules as for adverse events.

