8.3.2.2 Subjects lost to follow-up

If a patient cannot be contacted to collect follow-up information even beyond the 10 days from visit 3, he/she will be considered "lost to follow-up". But before declaring that a patient is "lost to follow-up", the Principal Investigator (or his/her team) must do his/her best effort to contact patients and attempts should be made via all available routes. A certified letter should be sent to the permanent address on file.

The methods used to attempt to contact the patient should be noted in the patient medical file.

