10.2.3. Impact of the treatment chosen on the risk to develop respiratory complication requiring antibiotics prescription

The impact of the treatment chosen on the risk to develop respiratory complication requiring antibiotic prescription during a 20-day follow-up period will be analysed by a multivariate logistic model. Subjects will be analysed on the FAS.

10.2.4. Impact of the treatment chosen on the intake of a conventional cold medication

The impact of the treatment chosen on the intake of a conventional common cold medication will be analysed on the FAS.

Common cold medications are antibiotics, antipyretics, mucolytics, decongestants, antitussives, systemic and topical corticosteroids.

The use/non-use of these medications (if the patient used it at least one day from D1 to D30, or if he/she never used it) will be modelled by a multivariate logistic regression.

The number of days of intakes of these medications is defined as follows:

- A day is counted when the patient used at least one of these medications this day;
- Each day is counted once, whatever the number of these medications used this day;
- The total number is the sum of all distinct days of use of these medications, from D1 to D30.

The number of days of intakes of these medications will be modelled by a multivariate Poisson regression.

The same analyses will be performed for each category of medications: antibiotics, antipyretics, mucolytics, decongestants, antitussives, systemic and topical corticosteroids.

10.2.5. Impact of the treatment chosen on the number of family members in close contact developing common cold symptoms

The impact of the treatment chosen on the number of family members in close contact developing common cold symptoms after the patient all over the study period will be analysed by means of a multivariate Poisson regression. Subjects will be analysed on the FAS.

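### The medication date rule in SAP 6.4.5 turns a missing stop date into days of use up to the child's trial end, and the day counts in SAP 10.2.4 include them

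*SAP*

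**What the plan says.** SAP 6.4.5 covers missing medication dates in one line: "Same rules as for adverse events". The rules it points to are in SAP 6.4.4.

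- **Scope of the end-date rule:** "the following rules concern events that are not “ongoing” at the end of the study". It therefore applies to a drug that is known to have been stopped.
- **No stop date at all:** "Completely missing date: it will be estimated by the reference end date".
- **Only the day missing, in the month of trial end:** "If the month/year = month/year of reference end date, it will be estimated by the reference end date". The same holds if day and month are both missing and the year is that of trial end. An incomplete date in an earlier month goes to the last day of that month.
- **No start date at all:** "Completely missing date: it will be estimated by the reference start date", which is the inclusion visit, D1.
- **Reference end date (SAP 6.4.1):** "The reference end date is the date when subject was determined to have ended the trial".

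SAP 10.2.4 defines two outcomes, each analysed overall and for seven drug classes. One is use or non-use: "if the patient used it at least one day from D1 to D30, or if he/she never used it". The other is the number of distinct days of use from D1 to D30, modelled by Poisson regression. No offset or exposure time is given, and no rule covers children not followed to D30. SAP 6.3.3 keeps dropouts in the analysis, leaves other missing data missing, and exempts dates from its no-imputation policy.

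**The concern.** Carrying an adverse event to trial end can be defended as cautious. SAP 10.4 gives the purpose of the adverse-event date imputation as deciding which events are treatment-emergent, a classification task. For medications the same rule does something else: the imputed interval becomes the outcome. An antipyretic or decongestant that the family says was stopped, without saying when, is credited with every day to the end of the child's trial.

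The end-date half of the rule seems to have little other use. Under SAP 8.2 and the note in SAP 10.3, a drug begun before the reference start date is classed as previous and one begun later as concomitant, so the start date decides. The stop date matters mainly for the day count.

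Medication intake is a stated secondary objective. The false days would enter the frequency distributions in mock Table 14.2.2.4.X and the Poisson models behind them. A second, separate gap is that children observed for different lengths of time enter both models as if all had been observed for 30 days.

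**Working it through.** **1. The plan's own figure.** The documents give none for the medication outcomes. The only sample-size figure is 100 per group for the primary AUC (d = 0.4, 80% power, two-sided 5%). It reproduces: n = 2(1.96 + 0.84)²/0.4² = 98, or 99 with unrounded quantiles and rounding up; 99.08 by the exact t-test, so 100. Power at 100 is 0.807 (normal) or 0.804 (t). This point does not touch it.

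**2. Days counted.** Let s be the start day and E the reference end day. A stopped course dated to E counts as min(E, 30) − s + 1 days. The 4-day true course is an assumption. With E at D30 or later:

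| Start | Days counted | False days | Shift in mean, 3 such children per 100 | 5 per 100 |
|---|---|---|---|---|
| D1 | 30 | 26 | 0.78 | 1.30 |
| D3 | 28 | 24 | 0.72 | 1.20 |
| D6 | 25 | 21 | 0.63 | 1.05 |

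Shift = number of children × false days / 100. The 3 and 5 children are illustrations.

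- Visit 3 is at D30±5. If the reference end date is D25, the counts are 25, 23 and 20, and the false days 21, 19 and 16.
- Month-only date: inclusion 2 October, trial end 1 November, stop known only as October. The rule gives 31 October, which is D30.
- A child who leaves at D10 after a 5-day course from D1 is counted to D10: 10 days, 5 of them false.
- In the overall count each day counts once, so overlap with another cold medicine reduces the excess.

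**3. Relative size among users.** Assume courses start on D1, last L days, and a share m have no stop date and count as 30 days. Mean = (1 − m)L + 30m.

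- L = 5: m = 2%, 5%, 10% gives 5.5, 6.25, 7.5 days, that is +10%, +25%, +50%. Over L = 3-10 and m = 2-10% the inflation runs from +4% to +90%.
- No true difference, L = 5, m = 5% against 10%: 7.5/6.25 = 1.20.
- Equal m = 5%, true lengths 4 and 5: (3.8 + 1.5)/(4.75 + 1.5) = 5.3/6.25 = 0.85, against a true 4/5 = 0.80. Equal missingness still dilutes a difference.
- Spread, with Poisson variation around L = 5 and m = 5%: variance = 0.95×5 + 0.05×0.95×25² = 34.4; divided by 6.25 this is 5.5. An unscaled Poisson test at nominal 5% would then reject in about 40% of null comparisons (formula 0.404; 4,000 simulations 0.402). The SAP states no dispersion term.

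**4. Use or non-use.** A course begun within D1-D30 makes the child a user whatever its stop date, so this outcome does not move.

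**5. Incomplete follow-up.** All rates here are assumed.

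- Days, constant daily use, a share d leaving at D10, no offset: mean ratio = (1 − d) + d×10/30, which is 0.967 at d = 5% and 0.933 at d = 10%.
- Use or non-use, if a leaver without a record were coded as a non-user: observed use = p(1 − d) + p·d·f, where f is the share of leavers' use recorded before leaving. With p = 60% and d = 5% against 15%, f = 0 gives 57% against 51%, an odds ratio of 0.79 with no true effect; f = 0.5 gives 0.89 and f = 0.8 gives 0.95. With equal dropout it stays 1.0.

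**The case against.** The best defence is that the case should be uncommon. Under Protocol 8.3.11, medication is entered in the e-diary, reviewed at both calls and validated by the investigator at Visits 2 and 3; Protocol 10.3 adds on-line checks and queries before lock. The documents give no rate of missing stop dates, and the illustrative numbers strain in seldom-used classes: if 10 of 100 children use a class, five undated courses means half its users. SAP 6.3.1 makes only the primary criterion conclusive and gives other p-values for information only. All of this stands, and it limits the size. It does not remove the rule, which gives a wrong count whenever it is applied to a short course.

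Several stronger readings are tempting, but the documents do not support them.

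- *Stop dates are ignored in general.* They are not: recorded dates are used as recorded, and only missing or partial ones are imputed.
- *A leaver with no drug recorded is a non-user to D30.* No rule says so. SAP 6.3.3 treats missing data as missing, and mock Table 14.2.2.4.X has a Missing row under both outcomes. What is absent is a rule for who belongs there.
- *A lost child's undated course always runs to D30.* Protocol 8.3.2.2 sets the label late ("If a patient cannot be contacted to collect follow-up information even beyond the 10 days from visit 3"), but does not make that the reference end date. SAP 6.4.3 lets the Validation Committee derive a missing end-of-study date from all recorded information, and Protocol 8.3.2.1 schedules a premature end-of-study visit for withdrawals. A date past D30 is one reading.
- *The groups report differently because spray users have an extra diary item.* Both groups keep the same medication diary, and nothing shows a difference.
- *The complication endpoint is distorted too.* Mock Table 14.2.2.3 is labelled as antibiotic use in follow-up, but SAP 10.2.3 speaks of a prescription for a complication and does not say that it is derived from medication dates.

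**Conclusion.** The point holds in a limited form. Read as written, SAP 6.4.5 with 6.4.4 extends a stopped medication with an incomplete stop date to the child's own trial end, and 10.2.4 counts those days up to D30. In a child followed to D30 this gives 30, 28 or 25 days for starts on D1, D3 or D6, of which 26, 24 or 21 are false if the true course was 4 days. How far group means move depends on the share of such courses, which the documents do not give; every group-level figure above rests on assumed rates.

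Bias between the groups in the null case needs unequal rates of missing stop dates, or unequal early leaving, and neither is shown. The second part is an omission: neither medication model allows for the time a child was observed. The primary analysis and the sample size are untouched. Because the outcomes are secondary and descriptive, this is a correction worth making rather than a threat to the trial's conclusion.

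**What to change.** **Stop dates.** Limit the 6.4.5 imputation to classifying a drug as previous or concomitant. For the day counts in 10.2.4, end a stopped course with an incomplete stop date at the last day on which its use was reported in the diary or at a call or visit, consistent with any known month and never later than last contact. Report the number of imputed stop dates by group, and keep the current rule as a sensitivity analysis. Removing imputed days from the main count also removes the extra spread shown above.

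**Incomplete follow-up.** Use log observed days within D1-D30 as an offset in the Poisson models. For use or non-use, apply one rule to every child with incomplete follow-up, whether or not use was recorded; time to first use, censored at last contact, is one option. Setting only the leavers without recorded use to missing would bias use upward. For example, take 100 children with 60% true use and 10 leavers, 4 of them with use recorded: (54 + 4)/94 = 61.7%.

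**Cost.** A few sentences in the SAP and slightly more programming. The documents do not show whether diary entries for medication are day by day or start and stop only; if the latter, calls and visits would have to supply more of the bound.
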